4.6 Analysis Population

- **Safety Population:** including all patients who have had a TURBT and have received treatment of study drug. The patients in safety population will be classified according to the actual treatment received, regardless of random assignment.

4.7 Final Analysis

The study was terminated early due to business reason and the final analysis will be performed for safety endpoints only.

5 STUDY PATIENTS

5.1 Disposition of Patients

Patients in defined populations as shown in **Section 4.6** and reasons for discontinuation will be summarized by randomized treatment arms.

5.2 Pretreatment Characteristics

Demographics, including gender, age, race, and smoking status will be summarized by actual treatment arms for patients in **Safety Population**.

6 EFFICACY EVALUATION

The study was terminated early due to business reason and analysis for efficacy endpoints will not be performed.

7 SAFETY EVALUATION

Safety endpoints will be evaluated for **Safety Population** and patients will be classified according to actual treatment received.

7.1 Extent of Exposure

Summary table and listing will be provided for instillation time from TURBT, volume of instillation, and duration of retention.

7.2 Concomitant Medications

Concomitant medications will be classified by WHO Drug Dictionary and be reported in listing.

7.3 Adverse Events

An overall summary table of treatment emergent adverse events (TEAE) will be provided. The summary will include any TEAE, TEAE by severity, SAE, TEAE and SAE leading to study drug discontinuation, any treatment-related AE, treatment-related AE by severity, treatment-related SAE, and treatment-related AE leading to study drug discontinuation.

7.3.1 Treatment Emergent Adverse Events

A TEAE is any AE that occurs from the first dose of study treatment until 35 days after the last dose of study drug administration. TEAEs will be graded according to National Cancer Institute

Common Terminology Criteria for Adverse Events (NCI CTCAE) version 4.03, and grouped by the MedDRA preferred term, and summarized by worst grade severity per patient by treatment arms.

The incidences of treatment emergent AEs will be presented by MedDRA SOC and PT with any grade and with Grade 3 or 4. Patients who experience more than one type of AE will be counted under each of the corresponding PT. Patients who experience different episodes of the same AE will be counted only once under the corresponding PT. Similarly, for determination of MedDRA SOC incidences, patients who experience multiple AEs under the same SOC will be counted only once for that SOC. Listing of all TEAEs will also be provided.

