The interim analysis will be performed by an Independent Data Monitoring Committee (IDMC) that will have access to the unblinded data. The study team will be blinded to the treatment allocation during the follow-up period.

All treatment-emergent adverse events will be graded according to National Cancer Institute Common Terminology Criteria for Adverse Events (NCI CTCAE) version 4.03, and grouped by the MedDRA System Organ Class and Preferred Term, and summarized by worst grade severity per patient.

Original Protocol: 22 Dec 2016

Study Flow Chart

Schedule of Study Assessments and Procedures

Assessments	Screening	Randomize/ Treatment	Safety Follow-up Visit ^a	Long-Term Post-TURBT Follow-up ^b									
	Day -30 to 1	Day 1	Day 35	Month								Every 6 Months	
				3 ^a	6	9	12	15	18	21	24		
	Visit 0	Visit 1	Visit 2	Visits 3-10								Visits 11+	
Informed Consent (IC)	x												
Urine cytology	x ^c			x	x	x	x	x	x	x	x	x	x
Cystoscopy	x ^c			x	x	x	x	x	x	x	x	x	x
Medical history	x												
Vital signs	x	x	x	x									
Weight and height	x												
Physical examination ^d	x		x	x									
Complete Blood Count	x	x ^e	x	x									
Chemistry	x	x ^e	x	x									
Pregnancy test	x												
Urine dip stick	x	x ^{e,f}	x	x	x	x	x	x	x	x	x	x	x
TURBT and Specimen Collection		x ^g											
Randomization		x											
Qapzola or Placebo instillation ^h		x											
Concomitant medications ⁱ	x	x	x	x	x	x	x	x	x	x	x	x	x
Adverse event assessment ^j	x	x	x	x	x	x	x	x	x	x	x	x	x

- a) Only patients who don't have pathology confirmed study-eligible NMIBC after TURBT, or patients who discontinue during follow-up, will return on Day 35 (±5 days) for the Safety Follow-up Visit. Patients in the Target Population will have the Safety Follow-up at the 3-month visit.
- b) Follow-up visits for patients with Ta histology are to be conducted every 3 months (±30 days) calculated from the date of TURBT for the first 2 years and then every 6 months (±60 days) until tumor recurrence or the End-of-Study, whichever occurs first.
- c) The qualifying cystoscopy and urine cytology may be performed up to 45 days prior to signing the informed consent.
- d) A complete physical examination will be performed at Screening and the Safety Follow-up Visit/Month 3 Follow-up Visit. At all other visits, a physical examination is only required as indicated.

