- e) If the screening assessments for the physical examination, hematology, chemistry, urine dipstick were performed within 3 days (72 hours) prior to Day 1/TURBT, these assessments do not need to be repeated at the Day 1 Visit. If patient is on anticoagulation therapy or has bleeding disorder risk, PT/PTT test should be ordered at Screening per investigator discretion.
- f) Urine dipstick to be done just prior to study drug instillation (60 ± 30 minutes) once gross hematuria is resolved.
- g) Each tumor/lesion resected during TURBT should be submitted to the local pathology lab in a separate container, noting the location, to ensure that the tumor location, size, stage, and grade for each tumor/lesion, according to the 2004 WHO/ISUP grading system along with the presence/absence of muscle fiber in the lesion, is assessed.
- h) Instillation of study drug (Qapzola or placebo) is to be performed at 60 ± 30 minutes post-TURBT procedure on Day 1 and is to be retained in the bladder for 60 ± 5 minutes.
- i) During the Follow-up Period, only medications to treat NMIBC will be recorded for concomitant medications.
- j) All adverse events from the time of study drug administration until 35 days after the last dose of study treatment will be recorded. From the 3-month visit through the End-of-Study, only deaths and AEs related to study procedures will be recorded.

TABLE OF CONTENTS

TITLE PAGE	1
INVESTIGATOR SIGNATURE.....	2
SYNOPSIS.....	3
TABLE OF CONTENTS	11
List of Figures.....	14
LIST OF ABBREVIATIONS AND DEFINITIONS OF TERMS	15
1 INTRODUCTION AND BACKGROUND	17
1.1 Non-Muscle Invasive Bladder Cancer	17
1.2 Qapzola for Intravesical Instillation	17
1.3 Clinical Studies with Qapzola	18
1.3.1 Clinical Efficacy of Qapzola	18
1.3.1.1 2-Year Recurrence Rate	19
1.3.1.2 Time to Recurrence	19
1.3.1.3 Other Secondary Efficacy Parameters	21
1.3.1.4 Time to Instillation	21
1.3.2 Clinical Safety of Qapzola.....	22
1.4 Study Rationale.....	23
2 STUDY OBJECTIVES	26
2.1 Primary Objective(s)	26
2.2 Secondary Objectives.....	26
3 INVESTIGATIONAL PLAN	26
3.1 Study Design and Treatment Plan.....	26
3.2 Study Duration	27
4 PATIENT POPULATION.....	28
4.1 Inclusion Criteria	28
4.2 Exclusion Criteria	28
4.3 Patient Discontinuation/Withdrawal Criteria.....	29
5 STUDY PROCEDURES	29
5.1 Screening.....	30
5.2 Patient Assignment	31
5.3 Timing of Assessments and Procedures	31
5.3.1 Screening	31
5.3.2 Treatment Period: Visit 1 (Day 1).....	32

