5.4.10 Adverse Event

At every visit, the Investigator or designee will question the patient about adverse events and intercurrent illnesses since the last visit, according to the National Cancer Institute (NCI) Common Terminology Criteria for Adverse Events (CTCAE) Version 4.03 for AE grading, and will record the pertinent information on the CRF.

From the time the study Informed Consent is signed through the day of study drug administration, only SAEs that are related to study procedures are to be recorded. For all non-Target population patients, all adverse events from the time of study drug administration until Day 35 (± 5 days) post-TURBT will be recorded. For Target population patients, all adverse events will be recorded from the time of study drug administration until the 3-month Follow-up Visit. Only deaths and AEs related to study procedures will be recorded from the 3 month visit until the End-of-Study.

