7.3.2 Treatment-Related Adverse Events

Assessment of relatedness to study drug for all AEs will be classified by investigators and reported. “Definitely related”, “probably related” and “possibly related” AEs will be considered as treatment related. An AE will be assigned as treatment-related if the relationship to study drug is missing.

The incidences of treatment-related AEs will be presented by MedDRA SOC and PT with any grade and with Grade 3 or 4.

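### Non-serious, unrelated AEs that start after Day 35 are recorded in Target patients up to Month 3 but fall outside the SAP's TEAE tables and listing, and the treatment-related table has no stated window

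*SAP*

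**What the plan says.** **Analysis window.** SAP 7.3.1 defines a TEAE as "any AE that occurs from the first dose of study treatment until 35 days after the last dose of study drug administration". The incidence tables by SOC and PT in that section are for TEAEs, and so is the general AE listing: "Listing of all TEAEs will also be provided". Protocol 7.2 contains the same 35-day definition.

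**Recording period.** Protocol 5.4.10 states: "For Target population patients, all adverse events will be recorded from the time of study drug administration until the 3-month Follow-up Visit". The Synopsis and Protocol 7.2 and 7.3.1 agree. Footnote j of the Schedule of Assessments differs: "All adverse events from the time of study drug administration until 35 days after the last dose of study treatment will be recorded".

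**Visits.** Footnote a of the Schedule reserves the Day 35 visit: "Only patients who don't have pathology confirmed study-eligible NMIBC after TURBT, or patients who discontinue during follow-up, will return on Day 35". For the rest, "Patients in the Target Population will have the Safety Follow-up at the 3-month visit". Footnote b places follow-up visits "every 3 months (±30 days) calculated from the date of TURBT for the first 2 years".

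**Treatment-related AEs.** SAP 7.3.2 speaks of AEs, not TEAEs, and names no time limit. It adds: "An AE will be assigned as treatment-related if the relationship to study drug is missing". Protocol 7.5 requires the investigator's causality assessment only up to 35 ± 5 days after treatment.

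**The concern.** The SAP drops every efficacy objective and keeps safety alone, so the AE outputs are the whole result. For Target patients who stay in the study, Month 3 is the one visit with a required post-dose physical examination, vital signs, CBC and chemistry (Schedule; Protocol 5.3.3 and 5.3.4). The TEAE window has already closed by then. A non-serious event that begins in between, or that is first found at Month 3 and dated to that visit, is recorded and then left out of the by-arm AE comparison. A delayed difference between arms in non-serious events could go unseen there.

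Other outputs only partly fill the gap. The SAP plans no physical-examination or vital-sign output. SAP 7.4 lists laboratory results but does not summarise them by arm, whereas Protocol 8.6.3 planned a worst-grade summary by arm.

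The second problem runs the other way. A later AE with blank causality could be counted as treatment-related while being absent from the TEAE tables, so the two sets of tables need not agree.

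**Working it through.** The plan gives no figure of its own here. The check is date arithmetic, followed by tracing each kind of event to an output.

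**Inputs.** TEAE limit: 35 days after dosing (SAP 7.3.1). Month 3 visit: 3 months ± 30 days from TURBT (footnote b). Instillation is on the day of TURBT, so one clock serves for both. Causality limit: at most 35 + 5 = 40 days (Protocol 7.5). The documents do not define a month, so three lengths are used as assumptions:
- 30 days;
- 365.25/12 = 30.44 days;
- (765 − 30)/24 = 30.63 days, taking the 765-day limit for the 24-month visit in Protocol 8.5.6.1 as 24 months plus 30 days.

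**Formulas.** Visit day d = 3 × month length, −30, +0 or +30. Days outside the TEAE window = d − 35. Share of recording days outside = (d − 35)/d.

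| Month length | Visit day d (early / nominal / late) | Days outside | Share outside |
|---|---|---|---|
| 30 | 60 / 90 / 120 | 25 / 55 / 85 | 42% / 61% / 71% |
| 30.44 | 61.3 / 91.3 / 121.3 | 26.3 / 56.3 / 86.3 | 43% / 62% / 71% |
| 30.63 | 61.9 / 91.9 / 121.9 | 26.9 / 56.9 / 86.9 | 43% / 62% / 71% |

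With whole calendar days, the nominal case is (91 − 35)/91 = 56/91 = 62%. Even the earliest permitted visit falls 25 to 27 days after the TEAE limit, and at least 60 − 40 = 20 days after the last day on which Protocol 7.5 requires causality. For non-Target patients seen within the visit window, the excess is at most 40 − 35 = 5 days.

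**Where each event goes (Target patient)**

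| Event | Output |
|---|---|
| Reported at Month 3, onset by Day 35 | TEAE tables and listing, because the definition follows onset |
| Recorded SAE, any onset | SAE listing, which has no stated window (SAP 7.3.3) |
| Start year missing | Assumed treatment-emergent (SAP 4.5) |
| Month 3 laboratory value | Laboratory listing (SAP 7.4) |
| Non-serious, onset after Day 35, judged related or causality blank | Unclear: possibly the treatment-related table |
| Non-serious, onset after Day 35, judged unrelated | No AE table or listing |

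**Population affected.** The plan expected 425/500 = 85% of patients to be Target. SAP 4.2 says recruitment was incomplete, so the actual share is unknown.

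**Conflict on collection.** The Synopsis and Protocol 5.4.10, 7.2 and 7.3.1 record all AEs to Month 3 in Target patients. Footnote j stops at 35 days. Protocol 7.7.1 records all SAEs only to Day 35 ± 5, then procedure-related ones. Protocol 5.3.4, whose heading includes Visit 3, mentions procedure-related AEs only, while 5.3.3 lists AE assessment at that same visit.

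**The case against.** The strongest reply is that the SAP follows the protocol. The 35-day definition is in Protocol 7.2, and the protocol's AE summaries (Synopsis and 8.6.1.1) are also built on TEAEs. This stands, and it weakens any charge that the SAP shortened the window. What did change is the endpoint label, from all AEs (Protocol 8.6.1) to all TEAEs (SAP 3.4.2). The Summary of Changes does not mention it.

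A reader might infer that everything first found at Month 3 drops out of the AE reporting. The documents do not support that. TEAE status depends on onset, and patients are asked about events since the previous visit (Protocol 5.4.10). SAEs are listed without a stated limit. The treatment-related table may also admit later events.

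A reader might also take 62% as the proportion of AEs lost. It is a share of days. The drug is a single instillation drained after about an hour, and in the two earlier Phase 3 studies both SAEs judged possibly related began on the day of instillation (Protocol 1.3.2). Related events may well cluster early.

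The mismatch with the treatment-related table is likewise a possibility and not an established pattern. SAP 7.3 places treatment-related AEs within the overall TEAE summary, which may imply the same window. Protocol 7.3.1 also asks for every AE to be classified by relationship, so later causality may be filled in.

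Finally, if sites followed footnote j, data after Day 35 are incomplete. This does not remove the gap, but it limits what an added table can show.

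**Conclusion.** The point holds in a limited form. Non-serious AEs judged unrelated, with onset after Day 35 and recorded up to Month 3 in Target patients, appear in no AE table or listing of a safety-only SAP. The uncovered stretch is about 56 of 91 recording days at a nominal visit, with a range of about 42 to 71%. The number of events affected cannot be derived from the documents. Whether later AEs judged related or lacking causality enter the treatment-related table is not settled by the SAP text.

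The conclusion assumes that the four protocol statements of recording to Month 3 governed practice, and that onset dates are known. A 35-day TEAE window is defensible as the main analysis. The weakness is that nothing reports the rest of what was recorded. The change is worth making, and it does not call the 35-day tables themselves into question.

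**What to change.** 1. Keep the 35-day TEAE tables and listing.
2. In SAP 3.4.2 and 7.3, add a summary by actual treatment arm and a listing of all recorded AEs from instillation through the Safety Follow-up Visit (Day 35 ± 5 for non-Target patients, Month 3 for Target patients). The SAP no longer has Target and Non-Target analysis sets, but the cut-off can be taken from each patient's own visit date.
3. In SAP 7.3.2, state which window the treatment-related table uses. Apply the missing-causality rule only to AEs within the period in which Protocol 7.5 required an assessment.
4. Reconcile the collection periods: the Synopsis and Protocol 5.4.10, 7.2 and 7.3.1 against footnote j and Protocol 7.7.1. Add a note to the new outputs that ascertainment after Day 35 may be incomplete where sites followed footnote j.
5. Name the move from all AEs to all TEAEs in the Summary of Changes.

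The cost is SAP wording and a little more programming on data that have been recorded, to the extent that sites collected AEs to Month 3. The drawback is that the longer window gives higher counts that include more background illness. Keeping the 35-day tables alongside makes this visible.

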7.3.2 Treatment-Related Adverse Events

Assessment of relatedness to study drug for all AEs will be classified by investigators and reported. “Definitely related”, “probably related” and “possibly related” AEs will be considered as treatment related. An AE will be assigned as treatment-related if the relationship to study drug is missing.

The incidences of treatment-related AEs will be presented by MedDRA SOC and PT with any grade and with Grade 3 or 4.

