7.3.1 Recording of Adverse Events

From the time the study Informed Consent is signed through the day of study drug administration, only SAEs that are related to study procedures are to be recorded. For all non-Target population patients, all adverse events from the time of study drug administration until Day 35 (± 5 days) post-TURBT will be recorded. For Target population patients, all adverse events will be recorded from the time of study drug administration until the 3-month Follow-up Visit. Only AEs related to study procedures and deaths will be recorded from the 3 month visit until a recurrence or the remainder of the follow-up period, whichever comes first.

All AEs should include resolution at the End-of-Study for a patient. The following conventions should be followed when patient completes or discontinues from the study

- If a patient dies, the date of death should be the date of AE stop for all ongoing AEs at the time of death.
- If a patient discontinues study drug due to an AE(s), the outcome of the AE is to be followed for 35 days (± 5 days) from the date of discontinuation or until the AE has returned to Grade ≤ 1 or returned to baseline conditions for the patient.

The status of the AE and the date of last contact with the patient will be captured. If the AE has not returned to Grade ≤ 1 or to Baseline conditions for the patient by the End-of-Study, the AE stop date should be left as ongoing.

All AEs will be classified by intensity/severity ([Section 7.3.2](#)), relationship to study drug ([Section 7.5](#)), and as serious or nonserious ([Section 7.7](#)).

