7.5 Relationship

The Investigator must make a causality assessment and document their assessment as to the relationship of all AEs and SAEs to study treatment for up to 35 days (± 5 days) after treatment (Table 3).

Table 3 Investigator Assessment of Adverse Event Causality

Relationship	Description
Not Related	The event is clearly related to factors other than study treatment, such as the patient’s clinical state, therapeutic interventions, or concomitant medications administered to the patient.
Unlikely Related	The temporal association, patient history and/or circumstances are such that the study drug or treatment is not likely to have had an association with observed event.
Possibly Related	The event follows a reasonable temporal sequence from the time of study treatment administration, and/or follows a known response pattern to study treatment, but could have been produced by other factors, such as the patient’s clinical state, therapeutic interventions, or concomitant medications administered to the patient.
Probably Related	The event follows a reasonable temporal sequence from the time of study treatment administration, and follows a known response pattern to study treatment, and cannot be reasonably explained by other factors, such as the patient’s clinical state, therapeutic interventions, or concomitant medications administered to the patient.
Definitely Related	The event follows a reasonable temporal sequence from the time of study treatment administration, and follows a known response pattern to study treatment, and cannot be reasonably explained by other factors, such as the patient’s clinical state, therapeutic interventions, or concomitant medications administered to the patient. In addition, the event either occurs immediately following study treatment administration, improves on stopping study treatment, reappears on repeat exposure, or there is a positive reaction at the application site.

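### SAP 7.3.2 counts a blank causality entry as treatment-related with no time limit, while the protocol is inconsistent on whether causality is required after Day 35 (±5)

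*SAP*

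**What the plan says.** SAP 7.3.2 expects an investigator judgement on every event: "Assessment of relatedness to study drug for all AEs will be classified by investigators and reported". Possibly, probably and definitely related all count as treatment-related, and blanks are then settled by default: "An AE will be assigned as treatment-related if the relationship to study drug is missing". The resulting output is described as follows: "The incidences of treatment-related AEs will be presented by MedDRA SOC and PT with any grade and with Grade 3 or 4". Neither the default nor the table carries an onset window or a restriction to TEAEs.

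The overall summary in SAP 7.3 also has related-event rows ("treatment-related AE by severity, treatment-related SAE"), but that table is introduced as a summary of TEAEs. SAP 7.3.1 ends the TEAE period 35 days after dosing.

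Protocol 7.5 makes the investigator document the "relationship of all AEs and SAEs to study treatment for up to 35 days (± 5 days) after treatment". Protocol 7.1 and 7.3.1 call for a causality classification of AEs with no time limit, although 7.3.1 points back to 7.5. Protocol 7.7.1 asks for causality in the initial SAE report.

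Under protocol 5.4.10, all AEs in Target patients are recorded to the Month 3 visit. After that: "Only deaths and AEs related to study procedures will be recorded from the 3 month visit until the End-of-Study". Non-Target patients have no AE recording after Day 35 (±5).

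**The concern.** Counting a blank as related is a reasonable conservative rule for an occasional gap. Here, one protocol section stops asking for the entry while AE recording continues, so some blanks may come from the protocol itself and not from carelessness. Take a urinary infection after the Month 12 cystoscopy, recorded only because it was procedure-related. If its drug-causality field is blank, SAP 7.3.2 as written makes it an AE related to an instillation given a year earlier.

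Safety is the only objective left in the SAP, and treatment-related AEs are a named endpoint in SAP 3.4.2. That entry lacks the TEAE qualifier carried by the first and fourth items in the same list. Events that nobody attributed to the drug would raise the related-AE count in both arms, placebo included, and blur what the table is meant to show. The default also departs, without saying so, from SAP 4.5, which limits imputation to partial dates.

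**Working it through.** The plan gives no figure to reproduce on this point. The check compares time windows, counted from Day 1 with 1 month = 30.4375 days.

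**Inputs**
- Causality window: 35 ± 5 days, so Day 40 at the latest (protocol 7.5).
- TEAE window: 35 days after dosing (SAP 7.3.1; protocol 7.2).
- Follow-up cystoscopies: every 3 months ± 30 days for 2 years, which is Months 3, 6, 9, 12, 15, 18, 21 and 24, or eight in all (protocol 5.4.8).
- Longest follow-up: no patient exceeded 24 months (SAP 3.3).

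**Do any scheduled cystoscopies fall inside the causality window?**
- Month 3, nominal: 3 × 30.4375 = Day 91.
- Month 3, earliest permitted: 91 − 30 = Day 61.
- Day 61 is later than Day 40, and every later visit is later still. All eight scheduled cystoscopies therefore fall outside both the causality window and the TEAE window.

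**How much of the recording period lies after the window?**
- Full follow-up: 24 × 30.4375 = 730.5 days.
- After Day 40: 730.5 − 40 = 690.5 days, and 690.5 / 730.5 = 0.945. About 95% of the period is after the window for a Target patient followed the full 24 months.

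**What is recorded in that period?**

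| Interval (Target patients) | Recorded (protocol 5.4.10) | Causality required by 7.5? |
|---|---|---|
| Instillation to Day 35 (±5) | All AEs | Yes |
| Day 40 to Month 3 visit | All AEs | No |
| Month 3 visit to End-of-Study | Deaths and procedure-related AEs | No |

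The middle interval is 91 − 40 = 51 days at the nominal visit. Across the ± 30-day allowance it runs from 61 − 40 = 21 to 121 − 40 = 81 days. Not only procedure-related AEs are exposed there. (Footnote j of the assessment schedule ends recording of all AEs at 35 days, so this interval is covered under protocol 5.4.10, 7.2 and 7.3.1 but not under that footnote.)

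**Which output is exposed?**
- SAP 7.3 overall summary: headed TEAE, so on a plain reading it excludes onsets after Day 35.
- SAP 7.3.2 SOC/PT table: described by relationship only, with no window. A late AE with a blank entry qualifies for it.

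**How many AEs?** This cannot be computed. The documents give no AE counts, no rate of missing causality and no CRF specification.

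**The case against.** The strongest reply is that the documents, taken together, do ask for causality on every AE. Protocol 7.1 and 7.3.1 set no limit, SAP 7.3.2 says the same just before stating its default, and 7.7.1 asks for it in SAE reports. An investigator who records a late AE because a procedure caused it can readily enter 'Not Related' from Table 3 of protocol 7.5. On that view the default only catches stray gaps, it is conservative, and it treats both arms alike in a descriptive analysis of a trial that ended early.

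Much of this stands. It limits the point to an inconsistency between 7.5 and the other sections. It does not remove it: 7.5 is the section that sets out the causality duty, 7.3.1 refers to it, and a site that stopped at Day 40 would be complying with it.

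Three stronger readings are tempting and are not supported:
- A reader might infer that the default would fire systematically. That requires the field to be left blank after Day 40, and nothing in the documents shows how the CRF handles it.
- A reader might put a rate on it. If 2% to 5% of cystoscopies each produced such a record, independently, then over eight visits 1 − 0.98^8 = 15% to 1 − 0.95^8 = 34% of patients would be affected. The 2% to 5% has no source in the documents. Eight visits is also the ceiling, because recurrence ends participation and non-Target patients are not followed.
- A reader might infer that the SAP 7.3 summary is contaminated too. Its TEAE heading argues against that.

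**Conclusion.** The point holds in a limited form. SAP 7.3.2 has an open-ended default, and protocol 7.5 conflicts with 7.1 and 7.3.1 on how long causality is required. All eight scheduled follow-up cystoscopies, and about 95% of a full 24-month follow-up, lie beyond the 7.5 window. Late AEs with blank causality would enter the 7.3.2 SOC/PT table as treatment-related in both arms, and that table could then disagree with the TEAE-based summary in 7.3.

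This rests on at least some sites reading 7.5 literally and on the CRF accepting a blank. The number of AEs cannot be derived from the documents, and it is near zero if the CRF forces an entry. Severity is minor: no hypothesis is tested, the rule applies to both arms, and it errs towards over-attribution.

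**What to change.** In SAP 7.3.2:
- Apply the missing-equals-related default only to AEs with onset inside the causality/TEAE window: instillation to Day 35, or to Day 40 if the ±5 allowance is adopted. State which.
- Keep every AE that the investigator marked possibly, probably or definitely related as treatment-related whatever its onset, and flag those that are not TEAEs. Cutting the whole table off at Day 35 would drop, for example, a Day 50 event judged probably related, and should be avoided.
- List later AEs with no entry as 'not assessed'.
- Note the default as an exception to SAP 4.5.

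Separately, reconcile protocol 7.1, 7.3.1 and 7.5 on how long a causality assessment is required.

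The cost is a few sentences of SAP wording and one flag, with no new data. The downside is that a late AE with blank causality appears in a listing and is no longer counted as related, which is less conservative for those events.
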